13.6.2 Statistical Analysis for the Primary Variable

13.6.2.1 Establishing Superiority of Test (T) and Reference (R) to Placebo

The hypotheses planned to be tested for the Superiority analysis are:

$$H_{01}: \mu_T = \mu_P \text{ vs. } H_{11}: \mu_T \neq \mu_P \text{ and}$$

$$H_{02}: \mu_R = \mu_P \text{ vs. } H_{12}: \mu_R \neq \mu_P$$

Sponsor: Lupin Inc.
Protocol no: TB-DPI-301

where μ_T = mean of baseline adjust FEV₁ AUC₀₋₂₄ for the Test Group and

μ_R = mean of baseline adjust FEV₁ AUC₀₋₂₄ for the Reference Group and

μ_P = mean of baseline adjust FEV₁ AUC₀₋₂₄ for the Placebo Group

Study sensitivity will be demonstrated if the Reference (R) product is shown to be statistically superior to Placebo (P) ($p < 0.05$ [two-tailed]). Efficacy of the Test product will be demonstrated if the Test (T) product is shown to be statistically superior to Placebo (P) ($p < 0.05$ [two-tailed]). For these comparisons, the repeated measures model described in [Section 13.6.1](#) will be applied to the ITT population.

13.6.2.2 Establishing Bioequivalence between Test (T) and Reference (R) products

The hypotheses planned to be tested for the BE analysis are:

$$H_0: \mu_T / \mu_R \leq 0.8 \text{ or } \mu_T / \mu_R \geq 1.25$$

$$H_1: 0.8 < \mu_T / \mu_R < 1.25$$

where μ_T = mean of the baseline adjusted FEV₁ AUC₀₋₂₄ for Test Group, and

μ_R = mean of the baseline adjusted FEV₁ AUC₀₋₂₄ for Reference Group

The analysis of the primary endpoint for BE will be the repeated measures analysis (described in the [section 13.6.1](#)) performed on the PP Analysis Set which will include all patients in the ITT population except those who had major protocol deviations.

The extension of Fieller's theorem to a 3-way crossover will be used as the primary method to assess the bioequivalence of the Test (T) and Reference (R) products. An analysis that applies Fieller's theorem only to the data of the Test (T) and Reference (R) products (i.e. ignoring data from the placebo treatment) will also be performed as a secondary method of analysis.

We use Fieller's theorem to create a $100(1-2\alpha)\%$ CI for $\theta = \mu_T / \mu_R$. The CI (θ_1, θ_2) will include all values of θ for which the above null hypotheses are rejected.

Fieller's theorem considers the quantity $G = Y_T - \theta * Y_R$, in which Y_T and Y_R are unbiased estimates of μ_T and μ_R . Note that $E(G) = 0$. We want to find all values of the parameter θ that do not reject $H_0: G = 0$ versus $H_1: G \neq 0$.

To do this computationally, we fit the crossover model to obtain the estimated means Y_T and Y_R (i.e., the estimated LSMeans). For this study, there are 6 treatment sequences with 3 periods, which gives the following LSMeans for μ_T and μ_R , respectively:

$$\text{LSmean (Test)} = \mu + \tau_T + 1/3(\pi_1 + \pi_2 + \pi_3) + 1/6*(\delta_1 + \delta_2 + \delta_3 + \delta_4 + \delta_5 + \delta_6) \quad (1)$$

$$\text{LSmean (Reference)} = \mu + \tau_R + 1/3(\pi_1 + \pi_2 + \pi_3) + 1/6*(\delta_1 + \delta_2 + \delta_3 + \delta_4 + \delta_5 + \delta_6), \quad (2)$$

Sponsor: Lupin Inc.
Protocol no: TB-DPI-301

where μ is the intercept, the τ 's are the treatment effects, the π 's are the period effects, and the δ 's are the sequence effects from the mixed model. The placebo data are included in the analysis but the placebo treatment effect, τ_P , is not needed in the bioequivalence assessment.

Writing G with equations (1) and (2):

$$G = (\tau_T - \theta * \tau_R) + (1 - \theta) [\mu + 1/3(\pi_1 + \pi_2 + \pi_3) + 1/6(\delta_1 + \dots + \delta_6)], \quad (3)$$

We use various values of θ to test $H_0: G=0$, and the $100(1-2\alpha)\%$ C.I. (θ_1, θ_2) is defined as largest/smallest values which do not reject the two α -level tests for H_0 above (Note: This is equivalent to a two one-sided tests procedure). The construction of the estimate statements in PROC MIXED will be based on equation (3), and will include data for all sequences, treatments and periods (i.e., placebo data will not be deleted). A sample SAS code for this mixed model is shown below, where the estimate statements are used to obtain the 90% confidence limits:

```
proc mixed data=<<dataset>>;
  class usubjid treatment period sequence;
  model auc0_24 = treatment period sequence / DDFM=SAT solution;
  repeated period /type = un subject = usubjid;

  *** Sample estimate statements ***;
  estimate ' 0.720' intercept 0.280 treatment 0 -0.72 1
    period 0.0933 0.0933 0.0933
    sequence 0.0467 0.0467 0.0467 0.0467 0.0467 0.0467 /alpha=0.05 upper;
  estimate ' 0.721' intercept 0.279 treatment 0 -0.721 1
    period 0.093 0.093 0.093
    sequence 0.0465 0.0465 0.0465 0.0465 0.0465 0.0465 /alpha=0.05 upper;
  estimate ' 0.722' intercept 0.278 treatment 0 -0.722 1
    period 0.0927 0.0927 0.0927
    sequence 0.0463 0.0463 0.0463 0.0463 0.0463 /alpha=0.05 upper;
  ...
  estimate ' 1.369' intercept -0.369 treatment 0 -1.369 1
    period -0.123 -0.123 -0.123
    sequence -0.061 -0.061 -0.061 -0.061 -0.061 -0.061 /alpha=0.05 lower;
  estimate ' 1.370' intercept -0.370 treatment 0 -1.37 1
    period -0.123 -0.123 -0.123
    sequence -0.062 -0.062 -0.062 -0.062 -0.062 -0.062 /alpha=0.05 lower;
  *** end of sample estimate statements ***;
  lsmeans treatment / alpha=0.05 cl diff cov;
run;
```

The Satterthwaite (DDFM=SAT) option provides the usual within-subject error degrees of freedom (DF) in the case of no missing data, and provides an adjustment to the error DF in the case of missing data. In either case, the error degrees of freedom will be quite large given the sample size of this trial so that the test statistic will have a near normal distribution.

Bioequivalence (BE) will be declared if the estimated 90% CI, (θ_1, θ_2) is entirely contained within the required BE limits of 0.80 to 1.25.

In addition to the 3-treatment effect model above, a separate analysis will be done using a 2-treatment approach, where Placebo (P) will be removed from the data. The construction of

Sponsor: Lupin Inc.
Protocol no: TB-DPI-301

the 90% C.I. (θ_1 , θ_2) will use the same approach as defined above, with only the 2 active treatments needed in the estimate statement.

The above approach is equivalent to a closed form solution created by Fieller's theorem which only requires the Test (T) and Reference (R) LSMeans estimates and their variances/covariances, and the critical value of the test statistic (T-test or Z-test).

13.6.2.3 Time to Maximum Bronchodilator Response

The time to maximum bronchodilator response (t_{\max}) is defined as the time post-dosing of the maximum FEV1 value for a patient. This will be summarized using descriptive statistics by treatment and sequence.

13.6.3 Subgroup Analyses

No subgroup analyses are planned for this study.

13.6.4 Multiplicity

In this clinical trial, the comparisons of interest are:

1. The superiority comparison between Lupin Tiotropium Bromide Inhalation Powder, 18 mcg (T) and Placebo (P)
2. The superiority comparison between SPIRIVA HANDIHALER, 18 mcg (R) and Placebo (P)
3. The bioequivalence comparison between Lupin Tiotropium Bromide Inhalation Powder, 18 mcg (T) and SPIRIVA HANDIHALER, 18 mcg (R)

As all 3 of these comparisons must be successfully achieved in order to demonstrate BE, no adjustment for multiplicity is required. The order of testing will be according to the list above.

13.6.5 Pooling of Sites

Pooling of sites is not planned for this study.

13.7 Safety Analyses

Safety analyses will be summarized by treatment for the safety population as defined in [Section 10.3](#) for Part 1 and Part 2 separately. Summary statistics (number of subjects, mean, standard deviation, median, minimum, and maximum) will be included for continuous variables. Summarizations of categorical variables will be presented in tabular form (number of subjects and percentages). Safety of drug regimen will be assessed for adverse events, serious adverse events (SAEs), COPD exacerbations, vital signs, physical examinations, HEENT and chest examinations, ECG recordings, SABA (albuterol/salbutamol MDI) and concomitant medication use.

Listings of all safety measurements will be provided.

Sponsor: Lupin Inc.
Protocol no: TB-DPI-301

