### 9.2.2.7 Electrocardiography

A 12-lead ECG will be performed for Part 1 and Part 2 as indicated in **Schedule of Events, Table 9-1**. For Part 1, the ECGs will be collected prior to lung function assessments. Procedures for conducting ECGs are described in the ECG manual. The patient should be in a supine position and resting for at least 5 minutes. A qualified physician at a central diagnostic center will be responsible for interpreting the ECG. However, at the screening visit (visit 1), the Investigator will preliminarily interpret the ECG to determine if the patient is eligible to proceed with screening assessments; final interpretation of the ECG will be the responsibility of the central ECG reader. The Investigator is responsible for determining whether an abnormality is clinically relevant.

Patients should have an ECG that is normal or free of clinically significant findings at the screening visit (visit 1) and visit 2.

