### 9.3.3 Double-blind Treatment Period (Part 1)

#### 9.3.3.1 Visit 2

Visit 2 is the beginning of the double-blind treatment period and will be conducted as day 0 and day 1.

The following procedures and assessments will be conducted at visit 2:

#### Day 0

- perform HEENT and chest examination
- perform 12-lead ECG, prior to measuring predose FEV1
- perform urine pregnancy test for all female patients of childbearing potential
- perform vital signs measurements (blood pressure, heart rate, respiration rate, and body temperature) prior to measuring predose FEV1

- perform predose FEV1 measurements at 0 hours (30 and 15 minutes before administration of study medication); see permitted spirometry windows in [section 9.2.1.1](#)
- Re-establish stability limits
  - Two stability limits (at home and investigational center) will be re-established (see [section 9.2.1.1](#)).
- demonstration of albuterol/salbutamol MDI and study medication inhaler technique
- assess inspiratory flow rate via In-Check DIAL device
- dispense/collect study medication
- review randomization criteria
- randomization via IRT
- administration of study medication at the investigational center
- check for issues with study inhaler
- perform serial FEV1 measurements at the following time points: 5 and 30 minutes postdose, and at 1, 2, 4, 6, 8, 10, and 12 hours postdose; see permitted spirometry windows in [section 9.2.1.1](#)
- dispense/collect albuterol/salbutamol MDI (as needed)
- dispense/collect placebo trainer
- review ed diary/electronic flow meter instructions
- assess ed diary data
- collect ed diary/electronic flow meter, as applicable
- record AEs
- record COPD exacerbations
- record concomitant medications/therapies

The patient will continue using the ed diary/electronic flow meter throughout the remainder of Part 1 and asked to measure their lung function (FEV1) in the morning prior to administering COPD medication at approximately the same time each day. Patients should not perform FEV1 measurements on the home device prior to day 1, visit 3 (both day 21 and day 22) and visit 4 (both day 42 and 43). Patients will be asked to record EXACT symptom scores (see [Appendix C](#)) and albuterol/salbutamol MDI in their ed diary.

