#### **11.5.7.4 HEENT, Chest Examination, and Electrocardiograms (ECG)**

For Part 1, during the double-blind period, abbreviated physical examination findings (HEENT and chest examinations) and ECG results will be summarized for any clinically significant findings and significant changes from visit 2.

For Part 2 of the study (open label extension), findings will be summarized for any clinically significant findings and significant changes from visit 2.

HEENT and chest examination findings will be summarized by five 3 by 3 shift tables where the shift is from visit 2 to each of the 4 visits during treatment, 2 visits in Part 1 and 2 visits in Part 2.

Electrocardiography (ECG) findings will be summarized by six 3 by 3 shift tables where the shift is from screening (visit 1) to each of the 6 visits during treatment, 3 visits in Part 1 and 3 visits in Part 2.

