9.3 Treatment, Washout and Follow-up

For summary purposes, treatment will be defined as days of dosing and days immediately after dosing, eg, day 0, 1, 21(+3), 22, 42(+3) and 43; washout will be days between treatments; follow-up is defined as 7 ± 3 days after visit 4 for Part 1, for patients who did not enter into the open-label Part 2 extension.

For Part 2, treatment is defined as first dosing date in Part 2 until the end of study or early termination (ET) for Part 2; follow-up is defined as 7 ± 3 days after visit 10.

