13.7.5 HEENT, Chest Examination, and Electrocardiograms (ECG)

For Part 1, during the double-blind period, abbreviated physical examination findings (HEENT and chest examinations) will be summarized for any clinically significant findings and significant changes from Visit 2. ECG results will be summarized by visit, and changes in overall clinical interpretation will be summarized.

For Part 2 of the study (open label extension), findings will be summarized for any clinically significant findings and significant changes from Visit 2.

Sponsor: Lupin Inc.
Protocol no: TB-DPI-301

HEENT and chest examination findings will be summarized by four 3 by 3 shift tables where the shift is from visit 2 to each of the 4 visits during treatment, 2 visits in Part 1 and 2 visits in Part 2.

Electrocardiography (ECG) findings will be summarized by four 3 by 3 shift tables where the shift is from screening (visit 1) to each of the 4 visits during treatment, 2 visits in Part 1 and 2 visits in Part 2.

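### SAP 9.3 and 13.7.3 count pre-dose vital signs (3 of 6 sets per patient in Part 1) under T, R or P, and SAP 13.7.5 plans four ECG shift tables for six scheduled visits

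*SAP*

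**What the plan says.** **Attribution of safety data.** SAP 13.7 opens with a general rule, "Safety analyses will be summarized by treatment for the safety population", and then lists the measures: "Safety of drug regimen will be assessed for adverse events, serious adverse events (SAEs), COPD exacerbations, vital signs", followed by the examinations, ECG recordings and medication use. For summary purposes, SAP 9.3 says "treatment will be defined as days of dosing and days immediately after dosing" and gives days 0, 1, 21, 22, 42 and 43 as examples. SAP 13.7.3 asks for Part 1 vital signs by treatment. It does not separate readings by time of dosing and names no baseline. SAP 9.1 sets the general baseline as the last value before dosing, without saying which of the three Part 1 doses is meant.

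**Timing.** In protocol 9.3.3, the vital-sign line for each dosing day (visits 2, 3 and 4) reads "respiration rate, and body temperature) prior to measuring predose" FEV1. Protocol 9.2.2.7 says of ECGs: "For Part 1, the ECGs will be collected prior to lung function assessments".

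**ECG tables.** SAP 13.7.5 says "ECG results will be summarized by visit" and plans four shift tables, in which "the shift is from screening (visit 1) to each of the 4 visits during treatment, 2 visits in Part 1" and 2 in Part 2. Protocol 11.5.7.4 plans six, from screening "to each of the 6 visits during treatment, 3 visits in Part 1 and 3 visits in Part 2".

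**The concern.** A by-treatment column should hold readings taken after that treatment was given. The SAP already applies this to adverse events: section 13.7.1.1 assigns an event to a product only if it occurs after dosing, on the treatment day or the next day. The vital-sign rule has no such condition, and the whole-day definition in 9.3 places readings taken before the dose inside the treatment window.

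The secondary objective in protocol 4.2 is safety and tolerability of the two active products after single doses. Part 1 is the only part in which Test (T), Reference (R) and Placebo (P) are compared. Protocol 3.2 names raised heart rate among the uncommon possible side effects of the Reference, so the vital-sign table is one that readers will look at. A column that mixes readings from before and after the dose, without a label, is hard to interpret.

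The ECG table count is a separate matter. Protocol section 11 gives the SAP precedence where the two differ, so the SAP's four tables would displace the protocol's six, and the SAP gives no reason for the reduction.

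**Working it through.** No power or alpha formula applies. The check is a count from the schedule (protocol Table 9-1, repeated as SAP Table 2) and the visit procedures in protocol 9.3.3 and 9.3.4.

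**ECG visits after screening, reproducing the protocol's figure first**
- Part 1: visits 2, 3 and 4 (days 0, 21, 42) = 3.
- Part 2: visits 7, 9 and 10 = 3.
- Total 3 + 3 = 6, which agrees with protocol 11.5.7.4.
- SAP 13.7.5: 2 + 2 = 4. Without a shift table: 6 − 4 = 2 visits.

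The SAP does not name its four visits. One explanation, which is an inference, is that the count came from the sentence just before it on HEENT and chest examinations. Those are scheduled at visits 2, 3, 4, 7 and 9. With visit 2 as baseline, the four later visits are 3, 4, 7 and 9. ECG differs in two ways: its shift baseline is screening, so visit 2 is a post-baseline visit, and it is also recorded at visit 10. On that reading the two missing tables are visits 2 and 10. Visit 10 is day 115, which is 115 − 43 = 72 days after Part 2 dosing with Test began, in about 120 patients.

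**Vital signs in the Part 1 treatment visits (screening and early termination excluded)**
- Sets per patient: days 0, 1, 21, 22, 42 and 43 = 6.
- Days 0, 21 and 42: taken before the pre-dose FEV1, which is itself measured 30 and 15 minutes before dosing. So 3 of 6 are pre-dose. The schedule footnote giving a 60-minute window around the pre-dose FEV1 does not fix the order, but the visit procedures do.
- Days 1, 22 and 43: the day after dosing. So 3 of 6 are post-dose, one per product. Day 43 is also the first day of Part 2, but protocol 9.3.4.1 gives the first Part 2 dose only after visit 4 procedures are complete. The day 43 set therefore still belongs to the third Part 1 treatment.

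**Part 1 ECGs**
- All 3 precede that day's dose, and none is scheduled on days 1, 22 or 43. The visit 2 ECG precedes any randomized dose. Those at visits 3 and 4 come at least 21 days after the previous one.

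**Rules against timing**

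| Data | SAP rule for Part 1 | After that day's dose |
|---|---|---|
| Adverse events | By treatment, only if after dosing (13.7.1.1) | All, by rule |
| Vital signs | By treatment, whole days (9.3, 13.7.3) | 3 of 6 sets |
| ECG | By visit (13.7.5); by treatment in the general sentence of 13.7 | 0 of 3 |

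**The case against.** Several points on the other side are sound.

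- **ECGs are not planned by product.** A reader might infer from the general sentence in SAP 13.7, or from the protocol synopsis, that pre-dose ECGs will appear in T, R and P columns and look alike whatever the drugs do. The documents do not support that. The specific section, 13.7.5, tabulates ECGs by visit, and the SAP prevails over the synopsis. All that remains is that the general sentence, read alone, says otherwise.
- **Calling these visits part of treatment need not mean post-dose.** The schedule heads visits 2 to 4 as the double-blind treatment period, and the ECGs there also serve the randomization and continuation criteria (protocol 6.3 and 6.4).
- **Pooling is not stated.** A reader might infer that a next-day vital-sign effect will be halved by averaging it with the pre-dose reading. That follows only if a table merges a visit's two days. No text says so, and SAP section 4.0 puts the table shells in a separate document, which may show time points separately.
- **A same-period baseline is a natural reading of SAP 9.1.** It is, but 13.7.3 neither states it nor calls for change from baseline.
- **Other safeguards exist.** Safety is descriptive with no testing (protocol 11.5.7). Clinically significant vital-sign worsening or ECG findings become adverse events (protocol 9.2.2.2 and 10.4.1.2), which follow the correct post-dose rule, and all safety measurements are listed.

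These points limit the consequence. They do not remove the whole-day definition applied to vital signs, or the mismatch in the ECG table count.

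**Conclusion.** The point holds as a minor one, in two parts. First, as written, SAP 9.3 with 13.7.3 counts 3 of the 6 Part 1 vital-sign sets per patient under a product not yet given in that period. This rests on the order of procedures in protocol 9.3.3. Any effect on the displayed results depends on a table layout that the documents do not show, so no size of dilution is claimed. Second, SAP 13.7.5 leaves two of six scheduled post-screening ECG visits without a shift table. That one of them is visit 10 is plausible but inferred.

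The absence of a post-dose ECG in Part 1 is a feature of the design that wording cannot change; the SAP can only label those ECGs correctly. The bioequivalence and superiority analyses are not affected.

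**What to change.** 1. **SAP 9.3:** split each dosing day at the time of dosing, as the adverse-event rule already does, and treat readings before the dose as that period's baseline.
2. **SAP 13.7.3:** present next-day vital signs, and their change from the same period's pre-dose set, by T, R and P.
3. **SAP 13.7.5:** keep ECGs by visit, label the Part 1 ECGs as pre-dose, exempt them from the general by-treatment sentence in 13.7, and plan six shift tables (visits 2, 3, 4, 7, 9 and 10).

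The cost is SAP wording, table labels and two more shift tables. It needs no new data, visits or staff, and the primary analysis does not change.

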13.7.1 Adverse Events

The adverse event (AE) data will be summarized separately for Part 1 and Part 2 of the study by treatment and total.

Summaries of treatment-emergent adverse events (TEAEs), including the number and percentage of events reported, the number and percentage of patients reporting at least one AE, at least one severe AE, at least one treatment-related AE, at least one SAE, at least one treatment-related SAE, at least one non-SAE, at least one AE leading to withdrawal, and at least one AE resulting in death will be presented by treatment. Treatment-emergent adverse events are those which first occur or increase in severity or relationship to study drug after the first dose of study drug after randomization.

A breakdown of the number and percentage of patients reporting each adverse event, categorized by System Organ Class (SOC) and Preferred Term (PT) according to MedDRA 20.0, will be presented by treatment. Note that counting will be by patient not event and patients are only counted once within each SOC or PT.

A further tabulation of these data, categorized by relationship to study drug, will be presented. Relationship to study drug is categorized as Related/Not Related as recorded on the CRF.

A summary of events reported, categorized by severity (Mild, Moderate and Severe), will also be provided. Patients with multiple events within a particular body system or preferred term will be counted under the category of their most severe event within that SOC or PT.

A summary of SAEs, AEs leading to discontinuation and AEs leading to death will be provided by treatment, study part and total, grouped by SOC and PT.

Adverse events (AEs) that occur before randomization will be summarized separately and will be listed. Those patients will not be part of the safety population.

All adverse events (including non-treatment-emergent events) recorded on the CRF will be listed.

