### 6.3 RANDOMIZATION CRITERIA

1. Patient continues to be in general good health, and continues to meet all study entry criteria.
2. Patient has not experienced an AE that would result in failure to continue to meet selection criteria.
3. Patient has had no significant changes in COPD medications or taken any prohibited medication during the screening and run-in period.
4. The patient has had no COPD exacerbation during the screening and run-in period as defined in [section 6.5](#).
5. Patient has withheld all inhaled SABAs for at least 6 hours and SAMAs for at least 8 hours prior to lung function assessments at visit 2.
6. Patient has not had a viral/bacterial URI or LRI during the screening and run-in period. A patient who develops symptoms of a URI or LRI during the screening and run-in period may rescreen no sooner than 6 weeks after resolution of symptoms, and at the discretion of the Investigator (see [section 9.3.7](#)).
7. Patient has not had clinically significant abnormalities as judged by the Investigator on the 12-lead ECG at visit 2.
8. Patient has no clinically significant laboratory abnormality as judged by the Investigator at the screening visit (visit 1).
9. Patient has demonstrated diary compliance to run-in medication within the margins of at least  $\geq 75\%$  and  $\leq 125\%$  of projected use.
10. Patient has completed diary data on a minimum of 5 days out of the last 7 days prior to randomization (not including the day of randomization) and achieved a minimum of 75% compliance with the diary during the single-blind run-in period.

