#### **11.5.7.1 Adverse events**

The number and percentage of patients experiencing at least one AE will be summarized by MedDRA, primary SOC, PT and LLT, by treatment and by intensity and relationship to study medication.

In Part 1, the blinded, single dose crossover part of the study, AEs will be tabulated by the following periods:

- double-blind treatment period
- during washout
- during follow-up

Adverse events (AEs) occurring after a study treatment during the treatment day and the day immediate after the treatment will be assigned to the relevant study treatment group.

Adverse events (AEs) that occur before randomization will be summarized separately and will be listed.

Narratives will be provided for SAEs.

Adverse events (AEs) will be tabulated separately for Part 2 of the study. For Part 2 of the study, AEs will be tabulated by the following periods:

- During the open-label study
- During follow-up (more than 24 hours after the last treatment day in the open-label study)

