**Revised text:**

In Part 1, the blinded, single dose crossover part of the study, AEs will be tabulated by the following periods:

- ~~pre-randomization~~
- ~~on or within 24 hours after a study treatment day double-blind treatment period~~
- during washout
- during follow-up (~~more than 24 hours after the last treatment day~~)

~~Adverse events (AEs) occurring on or within 24 hours after a study treatment day will be assigned to the relevant study treatment.~~

~~Adverse events (AEs) that occur before randomization for patients who are screen/randomization failures will be listed. Those patients will not be part of the safety population.~~

*Adverse events (AEs) occurring after a study treatment during the treatment day and the day immediate after the treatment will be assigned to the relevant study treatment group.*

*Adverse events (AEs) that occur before randomization will be summarized separately and will be listed.*

*Rationale for change: Adverse events (AEs) occurring on the day of treatment and the day immediately after treatment will be summarized by treatment instead of washout. Adverse events (AEs) will be summarized for all patients prior to randomization.*

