5.0 Introduction

This SAP describes the statistical methods to be used during the reporting and analyses of data collected under Lupin Inc. Protocol TB-DPI-301.

This SAP should be read in conjunction with the study protocol and CRF. This version of the plan has been developed using the protocol Amendment version 1 dated 11May2017 and CRF dated 14Mar2017. Any further changes to the protocol or CRF may necessitate updates to the SAP.

The SAP is to be developed in two stages. The purpose is to “finalize” a SAP so that PRA can start programming earlier in the process. Versions of the SAP up to initial sponsor approval will be known as SAP1. Changes following approval of SAP1 will be tracked in the SAP Change Log and a final version of the SAP, known as SAP2, will be issued for sponsor approval prior to database lock.

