10.3 Safety

The safety analysis population will include all patients who receive at least one dose of any one of the randomized investigational products and for whom data have been collected after randomization.

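### Two SAP safety-reporting errors: 13.7.1, read literally, drops dosed patients from the safety population, and 13.7.5 gives Part 2 two ECG shift tables for three ECG visits

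*SAP*

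**What the plan says.** **Safety population.** SAP 10.3 says that this population "will include all patients who receive at least one dose of any one of the randomized investigational products", provided data were collected after randomization. It has no exclusion for an earlier adverse event. SAP 13.7 adopts that definition: "Safety analyses will be summarized by treatment for the safety population as defined in" Section 10.3. SAP 13.7.1 then says that adverse events before randomization "will be summarized separately and will be listed. Those patients will not be part of the safety population". The matching sentence in protocol 11.5.7.1 reads "Adverse events (AEs) that occur before randomization will be summarized separately and will be listed" and adds no exclusion.

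**ECG shift tables.** SAP 13.7.5 plans four 3 by 3 tables, with the shift taken "from screening (visit 1) to each of the 4 visits during treatment, 2 visits in Part 1 and 2 visits in Part 2". In the same section, the Part 2 paragraph stands under a heading that covers HEENT, chest examination and ECG, and it measures significant changes from visit 2. SAP 9.1 sets baseline generally as the last value before dosing. Protocol 11.5.7.4 plans six ECG tables from visit 1, three in each part, but also describes ECG changes from visit 2.

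**The concern.** In 13.7.1 the words about patients leaving the safety population follow a sentence about events before randomization. The only group they can refer to is patients who had such an event. Some of those patients will go on to be randomized and dosed, and 10.3 counts them in. If a programmer followed 13.7.1, dosed patients would vanish from the safety tables. Safety and tolerability are the trial's secondary objective.

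In 13.7.5 the planned number of ECG tables does not match the number of ECG visits, and the reference visit is unclear. At least one on-treatment ECG visit in Part 2 would have no shift table. SAP 8.2 lists the 12-lead ECG among the safety variables followed in both parts.

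**Working it through.** **1. Can a patient with an adverse event before randomization be dosed?** Yes. Randomization criterion 2 in protocol 6.3 requires only this: "Patient has not experienced an AE that would result in failure to continue to meet selection criteria". A patient with any other event may be randomized. The literal reading of 13.7.1 and the definition in 10.3 therefore disagree about real patients.

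- The collection window before randomization is long enough for events to occur. Its minimum is the run-in alone, 14 days. Its nominal maximum is 30 (screening) + 3 (extra window for inhaled corticosteroid washout) + 14 + 2 (run-in) = 49 days.
- The documents give no event rate for this window, so no patient count follows.
- The protocol cannot silently correct the SAP, because protocol section 11 gives the SAP precedence where the two differ.
- The likely origin is visible in the amendment log (protocol Appendix D), which records superseded text and is not itself at fault. The same closing words once followed a sentence limited to patients who failed screening or randomization: "for patients who are screen/randomization failures will be listed. Those patients will not be part of the safety population". The SAP states its basis as follows: "This version of the plan has been developed using the protocol Amendment version 1 dated 11May2017". It carries the closing words without that limit.

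**2. How many ECG shift tables does the schedule imply?** The inputs are the ECG and HEENT rows of SAP Table 2. The visit lists in protocol 9.3.3 and 9.3.4 confirm the ECG visits.

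| Assessment | Part 1 visits | Part 2 visits | Tables from visit 1 | Tables from visit 2 | SAP 13.7.5 plans |
|---|---|---|---|---|---|
| ECG | 2, 3, 4 | 7, 9, 10 | 3 + 3 = 6 | 2 + 3 = 5 | 2 + 2 = 4 |
| HEENT/chest | 2, 3, 4 | 7, 9 | not done at visit 1 | 2 + 2 = 4 | 2 + 2 = 4 |

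The HEENT figure is reproduced exactly. The ECG figure is not reproduced under either baseline. The ECG sentence has the same 2 + 2 split as the HEENT sentence, although ECG has a visit 10 assessment and HEENT does not. The Part 1 count of two fits a visit 2 baseline but not the visit 1 baseline that the sentence names. The Part 2 count of two fits neither.

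**3. Which baseline?** The shift tables use visit 1, and the Part 2 paragraph uses visit 2. Under SAP 9.1, the last ECG before the first randomized dose is the visit 2 ECG. Protocol 11.5.7.4 mixes visits 1 and 2 in the same way, so it does not settle the question.

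**4. Which ECG loses its table?** The SAP does not say. If the ECG tables follow the HEENT visits, they fall at visits 7 and 9. Part 2 dosing starts on day 43, so on nominal days:

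- visit 7: 71 − 43 = 28 days of dosing
- visit 9: 99 − 43 = 56 days
- visit 10: 115 − 43 = 72 days, with no table

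The Part 1 ECGs are all taken before that day's spirometry and dose (protocol 9.2.2.7 and 9.3.3). Visits 7, 9 and 10 are therefore the only ECGs recorded during daily dosing.

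**The case against.** **The population conflict resolves itself.** SAP 13.7 applies 10.3, and protocol 11.3.3 and 11.5.7 agree with it. SAP 9.5 also counts as treatment-emergent an event already present at first dose that later worsens. That rule makes sense only if patients with an earlier event are in the tables. This stands as a reason to think the literal reading unlikely to be followed. It is also further evidence that the sentence is wrong.

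**Two Part 1 ECG tables could be right from visit 1.** The visit 2 ECG precedes any randomized dose, so it might not count as a visit during treatment. This does not stand. SAP 9.3 counts day 0 as a treatment day, SAP 13.7.3 calls visits 2 to 4 treatment visits, and protocol 11.5.7.4 uses the same counting phrase from visit 1 to reach three in Part 1. It would in any case leave Part 2 one short.

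**The two baselines are an ambiguity rather than a contradiction.** In 13.7.5 the Part 1 comparison with visit 2 is tied to HEENT and chest only, and the Part 2 paragraph speaks of findings without naming ECG. That is a fair qualification. The heading covers ECG, however, and 9.1 points to visit 2, so the reader still cannot tell which reference applies.

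**The stakes are small.** Protocol 4.2 and SAP 6.0 word the secondary objective around single doses, and the stated Part 2 objectives concern the device. Significant Part 2 findings are still summarized and all safety measurements are listed. The table shells are a separate document that may already be right. All of this stands and sets the weight of the point.

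**Conclusion.** Both errors hold, and both are minor.

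SAP 13.7.1, read literally, excludes dosed patients whom 10.3 includes. The intended meaning was very probably patients who failed screening or randomization, so the practical risk is low. Its size in patients cannot be given.

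SAP 13.7.5 plans four ECG shift tables where the schedule gives six (visit 1 baseline) or five (visit 2 baseline). The shortfall of one table in Part 2 does not depend on the baseline. That the missing table is visit 10 is an inference from the HEENT pattern, and the day counts of 28, 56 and 72 are nominal and ignore visit windows. No data are lost, and neither error touches the primary endpoint, power or sample size.

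**What to change.** 1. In SAP 13.7.1, delete the sentence about the safety population, or limit it to patients who were never randomized and dosed.
2. In SAP 13.7.5, state one ECG baseline and reconcile it with the Part 2 paragraph and SAP 9.1.
3. Match the table count to that baseline. From visit 1 there are six tables (visits 2, 3, 4, 7, 9, 10), as in protocol 11.5.7.4; the visit 2 table would then compare two ECGs taken before any randomized dose. From visit 2 there are five (visits 3, 4, 7, 9, 10). Visit 10 is included either way.

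The cost is one sentence, one baseline statement and one count. All the data are already scheduled for collection. The separate table shells were not available here and should be checked against the corrected count.
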